8.3 Definitions

Baseline measurements are the last recorded values for each parameter prior to the Initial Fitting Visit. Baseline diary measurements, such as average numbers of FI episodes, are based on the entire Baseline Diary. Other assessments are typically recorded at Visit 1.

Change from baseline is calculated as result – (baseline result).

Percent change from baseline is calculated as 100^* (change from baseline) / (baseline result). This statistic is represented in tables by % Δ .

Study day is calculated as date – Visit 4 date, for visits occurring prior to Visit 4 (the beginning of the Treatment Period), and calculated as date – Visit 4 date + 1, for visits on or after Visit 4. Study day will not be presented for screen failures.

All calculations based on diary data will be calculated based on the entire reported diary period, if the diary was completed for that time period (12+ days for Baseline and Test diary, 10+ days for 3, 6, and 12 month diaries as per Section 8.2). If >14 days were completed for any time period, only the first 14 days will be used for computations. If a diary was repeated as allowed per protocol or Sponsor-approved Protocol Deviation, the calculations will be performed on the repeat diary information only.

A **bowel movement (BM)** is defined as any passing of stool reported as a "normal (continent) BM", "minor soil" or "major soil". Staining episodes will be omitted from this definition.

A fecal incontinence (FI) episode is defined as any passing of stool reported as a "minor soil" or "major soil". Staining episodes will be omitted from this definition.

Loose stool is defined as a BM with a Bristol stool score of 6 or 7. **Solid stool** will be defined as a BM with a Bristol stool score of 1-5.

The following statistics will be calculated from diary data, for each diary period:

- Average number of FI episodes per week: 7 * (# episodes) / (# days of diary entry)
- Average number of FI episodes while insert in place, per week: 7 * (# episodes while insert is in place) / (# days of diary entry)
- Average number of FI days per week: 7 * (# days with ≥1 FI episode) / (# days of diary entry)
- Average number of urgent BMs per week: 7 * (# urgent BMs) / (# days of diary entry)
- Average number of BMs per week: 7 * (# BMs) / (# days of diary entry)
- Average number of loose stool BMs per week: 7 * (# BMs with Bristol stool scale score of 6 or 7) / (# days of diary entry)
- Average number of solid stool BMs per week: 7 * (# BMs with Bristol stool scale score of 1 5) / (# days of diary entry)
- Average number of BM days per week: 7 * (# days with ≥1 BM) / (# days of diary entry)
- Average number of episodes per week: 7 * (# episodes) / (# days of diary entry). Episodes include both BM episodes (normal, minor FI, and major FI) and staining episodes.

- Average proportion of episode type: (# episodes of that type) / (# total episodes), where episodes includes both BM episodes and staining episodes
- Average Bristol score: (sum of Bristol scores) / (# BMs)
- Average proportion of loose stools: (# BMs with Bristol stool scale score of 6 or 7) / (# BMs)
- Average proportion of solid stools: (# BMs with Bristol stool scale score of 1 5) / (# BMs)

Treatment response is defined as having a ≥50% reduction in the average number of FI episodes per week on the Treatment Diary (3, 6, or 12 months) as compared to the associated Baseline diary.

Subjects are classified into **FI phenotypes** based on the results of the FIQOL at Baseline. Subjects ranking question 2k, "I can't hold my bowel movement long enough to get to the bathroom", as more severe than question 2l, "I leak stool without even knowing it", are classified as *urge-predominant*. Those ranking question 2l as more severe than question 2k are classified as *passive-predominant*. Those ranking both questions the same, when the result is "most of the time" or "some of the time", are classified as *both* predominances. Those ranking both questions as "a little of the time", "none of the time", or "N/A" will not be categorized as having an FI phenotype.

8.4 Interim Analysis

No formal interim analyses are planned.

The sponsor may choose to perform ad hoc analyses during the course of the study. These will not be considered formal interim analyses, and no adjustments to alpha spending will be made.

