3.11 Power and Sample Size Considerations

Power calculations were performed based on the primary effectiveness analysis, which tests whether the fraction of treatment responders is significantly greater than 0.40 ($H_0: \pi \leq 0.40$ vs. $H_A: \pi > 0.40$) using a one-sided exact binomial test, based on significance $\alpha = 0.025$ and power $1 - \beta = 0.90$.

Based on the LIFE study, we anticipate an 85.6% success rate among study completers and conservatively estimate 21.3% dropout within 3 months, resulting in an estimated 67% response rate in this study. With as few as 40 subjects in the ITT cohort, the study has $\geq 90\%$ power to detect a response rate greater than 40%. Additional subjects, up to the maximum of 150 subjects, will be enrolled through a specified end date in order to provide a more robust analysis.

Withdrawal from the study during the Screening Period is estimated to be quite high due to the baseline diary completion and device fitting requirements. Subjects who are successfully fit with the Eclipse System and successfully complete the Screening Period will be eligible for treatment. Therefore, an estimated 160 to 600 subjects may be recruited into this study in order to achieve 40 to 150 subjects who successfully enter the Treatment Period.

We estimate the subject dropout rate between the start of the Treatment Period and the 12 month visit to be 33%, yielding approximately 25 to 100 subjects completing 12 months of study participation. In a 12 month study of non-surgical management of stress urinary incontinence the dropout rate over this same time period was approximately 36%.²⁹

4 Adverse Events

Investigators and the Sponsor will carefully track and report adverse events. Any subject who is exposed to the Eclipse System, including the Eclipse Insert, the Trial Insert or Sizers (has any Eclipse System device inserted into their vagina) will be included in the Safety Cohort and Safety Endpoint Analysis.

Adverse event definitions are provided in **Table 4**. Based on clinical experience to date the expectation is a very low risk of serious or unanticipated device-related adverse events.

Table 4. Adverse Event Categories

Term	Definition

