2.3 Recruitment	Clarified that enrollment may be stopped or paused at any time by the Sponsor. Revised individual site enrollment contribution levels from a number cap to a percent of total launched. Removed statement that enrollment may be restricted by sub-group.	Each site is expected to enroll a minimum of 10 and a maximum of 30 treatment-eligible subjects...Enrollment is competitive until overall enrollment target is reached, and recruitment may be restricted by sub- groups to ensure approximately one half of the subjects entering the Treatment Period are <65 years of age and one half are >65 years of age.	Each site is expected to contribute approximately 7-25% of the total treatment-eligible subjects...Enrollment is competitive until overall enrollment target is reached or study termination by the Sponsor.

CONFIDENTIAL - THIS DOCUMENT CONTAINS CONFIDENTIAL AND PROPRIETARY INFORMATION THAT IS THE PROPERTY OF PELVALON, INC. NEITHER THIS DOCUMENT NOR THE INFORMATION HEREIN MAY BE REPRODUCED, USED, OR DISCLOSED TO ANY THIRD PARTY WITHOUT THE PRIOR WRITTEN CONSENT OF PELVALON, INC.

Section	Description of Change	Rev C – 10 Dec 2015	Rev D – 09 Feb 2017
3.6 Primary Effectiveness Analysis	Removed references to absolute enrollment numbers to reflect potential interim analyses.	The null hypothesis will be rejected if 72/150 of subjects exhibit treatment response at the 3 month time point.	The null hypothesis will be rejected if a sufficient percentage of subjects exhibit treatment response at the 3 month time point.

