6.2 Power and Sample Size

As described in Section 3.11 of the study protocol, power calculations were performed based on the primary effectiveness analysis, which tests whether the fraction of treatment responders is significantly greater than 0.40 (H₀: $\pi \le 0.40$ vs. H_A: $\pi > 0.40$) using a one-sided exact binomial test, based on significance $\alpha = 0.025$ and power $1 - \beta = 0.90$.

Based on the LIFE study, we anticipate an 85.6% success rate among study completers and conservatively estimate 21.3% dropout within 3 months, resulting in an estimated 67% response rate in this study. With as few as 40 subjects in the ITT cohort, the study has ≥90% power to detect a response rate greater than 40%.

Telephone follow-up calls are required in between each Treatment Visit.

⁺ If clean catch urine test is positive, the test must be repeated until either it, or a urine culture test, is negative before performing a Fitting Visit (Visit 2)

[†] If clinically indicated.

[‡] AEs recorded starting at the first Fitting Visit (Visit 2); Con Meds recorded at baseline and reviewed / updated at every visit.

^{††} A pelvic exam and Device Satisfaction questionnaire are required at all early study exit visits after the first Fitting Visit (Visit 2).

Additional subjects, up to the maximum of 150 subjects, will be enrolled through a specified end date in order to provide a more robust analysis.

Withdrawal from the study during the Screening Period is estimated to be substantial due to the baseline diary completion and device fitting requirements. Subjects who are successfully fit with the Eclipse System and successfully complete the Screening Period will be eligible for treatment. Therefore, an estimated 160 to 600 subjects may be recruited into this study in order to achieve 40 to 150 subjects who successfully enter the Treatment Period.

We estimate the subject dropout rate between the start of the Treatment Period and the 12 month visit to be 33%, yielding approximately 25 to 100 subjects completing 12 months of study participation. In a 12-month study of non-surgical management of stress urinary incontinence the dropout rate over this same time period was approximately 36%.¹

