7.2 Analysis Populations

The Safety Population will include all subjects exposed to any part of the Eclipse System during or after Visit 2 (Initial Fitting Visit). This will include all subjects who

were unsuccessfully fitted, and screen failures. This will be the primary analysis population for all safety analyses.

The Test Population will include all subjects who are successfully fit with the Eclipse Insert and successfully completed a Test Diary.

The Intent-to-Treat (ITT) Population will include all subjects who are successfully fit with the Eclipse Insert, successfully complete Visit 4, and enter the Treatment Period.

The Per-Protocol (PP) Population include all subjects in the ITT population who complete Visit 5, complete at least 10 out of 14 consecutive days of diary data at the 3 month visit, and have no major protocol deviations.

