11.1 Primary Analysis

The primary analysis will test the following statistical hypotheses for the observed response rate:

$$H_0$$
: $\pi = 0.40$

$$H_A$$
: $\pi > 0.40$

where π is the observed proportion of subjects who are treatment responders at the 3 month time point. An exact binomial test will be used to evaluate whether the response rate is significantly larger than 40%, based on the ITT population. Treatment response is calculated as defined in Section 8.3.

The number and proportion of treatment responders, and its 95% confidence interval, using exact (Clopper-Pearson) confidence limits, will be presented. A p-value for the one-sided upper-tail test of whether the proportion is significantly larger than 0.40, will also be presented. The null hypothesis will be rejected if a sufficient percentage of subjects exhibit treatment response at the 3 month time point. As described in Section 8.2, subjects with missing information will be treated as non-responders for this analysis.

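### Do the unadjusted ad hoc analyses allowed by SAP 8.4, with final N open between 40 and 150, undermine the one-sided 2.5% level?

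*SAP*

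**What the plan says.** SAP 8.4 opens with "No formal interim analyses are planned". It then allows the sponsor to carry out ad hoc analyses while the study runs and adds: "These will not be considered formal interim analyses, and no adjustments to alpha spending will be made". It does not limit their number, timing, endpoint or use.

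SAP 6.2 justifies power at 40 ITT subjects and says that further subjects, "up to the maximum of 150 subjects, will be enrolled through a specified end date". Protocol 3.11 has the same rule and gives its purpose: more subjects "will be enrolled through a specified end date in order to provide a more robust analysis". Neither document prints the date.

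On the test itself, SAP 11.1 says: "An exact binomial test will be used to evaluate whether the response rate is significantly larger than 40%, based on the ITT population". SAP 7.2 places in the ITT population every woman who is successfully fitted and goes on to "successfully complete Visit 4, and enter the Treatment Period". SAP 8.2 counts those without an adequate diary as non-responders. SAP 8.1 sets a one-sided 2.5% level for the primary endpoint and makes all other p-values descriptive. The rejection rule is worded without a count: "The null hypothesis will be rejected if a sufficient percentage of subjects exhibit treatment response at the 3 month time point".

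**The concern.** A fixed-sample exact test holds its level only if the sample size does not depend on the outcome. Several features together suggest that it might. The trial is open-label with one arm, so any tabulation of 3-month response is an unmasked look at the primary endpoint. Final N is open over a wide range. The closing date is not shown, and SAP 6.1 also lets enrolment end on termination by the sponsor. The revision record in Protocol section 8 explains the count-free rejection rule in these words: "Removed references to absolute enrollment numbers to reflect potential interim analyses". No sentence states that ad hoc looks may not influence when enrolment closes.

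If the sponsor could look repeatedly and close enrolment at a favourable moment, the nominal 2.5% would understate the chance of a false claim. The primary test is the only confirmatory inference in the trial, so that chance would matter.

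**Working it through.** **Inputs.** Null rate 0.40, one-sided level 0.025, exact binomial test (SAP 6.2, 8.1, 11.1). Assumed response: 0.856 × (1 − 0.213) = 0.674, stated as 67% (SAP 6.2). N from 40 to 150 (SAP 6.2).

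**The plan's own figure.** The critical count is the smallest r with P(X ≥ r | N, 0.40) ≤ 0.025. At N = 40, r = 23, with size 0.0189 and power 0.924 at 67%. The stated power of at least 90% reproduces.

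**Is the rejection rule undefined?** No. The level, the null rate and the exact test fix r for any N: 23 of 40, or 73 of 150 (size 0.0193). Removing a numeral from the text removes nothing from the rule.

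**The plan as written.** Enrolment stops on a date or at 150, and all ITT subjects are tested. For a fixed N, the exact size over N = 40 to 150 runs from 0.0120 (N = 45) to 0.0248 (N = 122). It never exceeds 0.025, so not knowing N in advance costs nothing. Looks that leave N and the final test alone do not alter this.

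**The departure that would do harm.** Suppose enrolment closes at the first look with p ≤ 0.025. Women already in treatment but short of 3 months still belong to the ITT population. The test is therefore made at min(look + pending, 150), against the critical count for that N. The documents give neither a look schedule nor an accrual rate, so both are assumptions here. Type I error at a true rate of 40%, in percent, by exact recursion:

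| Pending | Looks 40, 150 | 40, 95, 150 | 40, 75, 110, 150 | every 10 from 40 | every subject from 40 |
|---|---|---|---|---|---|
| 5 | 2.57 | 3.02 | 3.41 | 4.30 | 4.16 |
| 10 | 2.58 | 3.01 | 3.17 | 3.54 | 3.59 |
| 20 | 2.27 | 2.68 | 2.84 | 2.96 | 3.22 |
| 30 | 2.31 | 2.46 | 2.65 | 2.72 | 2.85 |
| 40 | 2.13 | 2.30 | 2.36 | 2.44 | 2.57 |

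Seven of the 25 cells are below 2.5%. At 50 pending the range is 2.2% to 2.4%, and at 60 it is 2.0% to 2.3%. The values do not fall smoothly, because the exact critical counts are discrete: 7 pending gives up to 4.5%. The table is therefore an illustration, not a bound. Ignoring pending women altogether gives 3.48% (looks at 40 and 150) to 8.70% (every subject), but that would not be the ITT test of SAP 11.1.

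**Which rows are plausible?** Pending number ÷ 3 months gives entries per month. Five pending means 5/3 ≈ 1.7 a month, so going from 40 to 150 would take 110/1.67 ≈ 66 months, with up to 15 sites planned. Forty pending means 40/3 ≈ 13 a month. The 5 to 7 weeks of screening would add to the pending group if women already in screening may still enter. Taking 3 months as 13 weeks, the addition is 5/13 to 7/13, or 38% to 54%. Both points favour the lower rows.

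**At the planned rate.** With a true response of 67%, the same scenarios reject with probability 97.56% to 99.96%.

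**The case for a change.** The best case for a change is that calling a look informal does not control error; what the look is used for does. An open N is harmless alone, and so are unadjusted looks. The plan has both, with no sentence keeping them apart and no printed date. One sentence would let a reader rely on the 2.5% without asking how the looks were used.

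Part of this stands. No passage bars a look from influencing the closing date, and if that happened the level would not be guaranteed. A reader of the results may reasonably ask when the date was fixed.

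The rest does not carry. The plan does state a closing rule, by date and cap, and gives its purpose as a more robust analysis rather than reaching significance. Harm requires departing from that rule. Declining to spend alpha is correct for looks that carry no decision. The entry in the revision record speaks only of potential interim analyses, while the current SAP plans none, so it is not evidence of outcome-driven stopping. A spending function would answer an early efficacy claim that the plan does not make. The calculation also models only closing on success; closing for low response or for reasons unrelated to response would not inflate the error.

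**Conclusion.** The concern is true only as a conditional statement, and it calls for no change. Followed as written, the plan holds its level: exact size is at most 0.0248 for every N from 40 to 150. What is absent is detail, namely the calendar date and an explicit statement that it does not depend on response. A competent analysis team would supply both by running the primary test once on all ITT subjects at the stated close.

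If a look did move the closing date, type I error would be about 2.1% to 4.3% on the tabulated schedules with 5 to 40 pending, and below 2.5% at 50 or more. That would matter only if the true response rate were near 40%. Every woman in the ITT population has already shown at least a 50% reduction on the Test Diary, and the plan expects 67%, where the conclusion would hardly change. These figures rest on assumed look times and pending numbers, on closing triggered by success, and on a single final test of the whole ITT population.

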8.5 Pooling Strategy for Study Sites

Data for all sites will be pooled for all safety and efficacy analyses. Study diary success rates per study period may also be summarized by study site in order to evaluate the consistency of effect of treatment by site.

8.6 Visit Windows/Unscheduled Visits

All data will be listed and summarized by the nominal visit. No visit windowing will be performed.

9 DEMOGRAPHICS AND BASELINE CHARACTERISTICS

All summaries of demographic information will be based on the ITT population.

Demographic information, including age (calculated as the difference between date of informed consent and birthdate, in years), body mass index (BMI), and race/ethnicity, will be summarized. The number and percentage of subjects <65 years of age and ≥ 65 years of age will also be presented.

Medical history such as types of previous urogenital surgeries, current or recent sexual activity, parity, menopause status, Digital Rectal Examination Scoring System (DRESS) resting and squeeze scores, and comorbidities will also be summarized.

Baseline FI characteristics such as FI type, duration of symptoms, previous treatments, self-management, and etiology will also be summarized.

10 CHANGES IN CONDUCT OR PLANNED ANALYSES FROM THE PROTOCOL

This analysis plan was developed in conjunction with CA005 Protocol Revision D, dated 09 Feb 2017. No changes in conduct or planned analysis have occurred.

11 EFFICACY

The ITT population will be used as the primary analysis population for efficacy analyses. The PP population is used as a supportive analysis where specified.

11.1 Primary Analysis

The primary analysis will test the following statistical hypotheses for the observed response rate:

$$H_0$$
: $\pi = 0.40$

$$H_A$$
: $\pi > 0.40$

where π is the observed proportion of subjects who are treatment responders at the 3 month time point. An exact binomial test will be used to evaluate whether the response rate is significantly larger than 40%, based on the ITT population. Treatment response is calculated as defined in Section 8.3.

The number and proportion of treatment responders, and its 95% confidence interval, using exact (Clopper-Pearson) confidence limits, will be presented. A p-value for the one-sided upper-tail test of whether the proportion is significantly larger than 0.40, will also be presented. The null hypothesis will be rejected if a sufficient percentage of subjects exhibit treatment response at the 3 month time point. As described in Section 8.2, subjects with missing information will be treated as non-responders for this analysis.

11.2 Secondary Endpoint Analysis

The following analyses will be considered secondary efficacy analyses:

11.2.1 Treatment Response

The primary analysis will be repeated at the 6, and 12 month time points, based on the ITT population. Subjects with missing treatment response information at a time point will be considered non-responders, as described in Section 8.2.

The primary analysis will be repeated at the 3, 6, and 12 month time points, based on the PP population for those time points. Subjects with missing treatment response information at a time point are excluded from the analysis of the PP population at that time point, as described in Section 8.2.

11.2.2 PGI-I

Subjects will rate their control of bowel leakage, as compared to how it was before the Eclipse System, on a 7-point scale (1=Very Much Better, 7=Very Much Worse) at the 3, 6, 9, and 12 month visits.

Scores may be summarized by time point, both continuously and by number and percent of subjects selecting each response, using the PP population.

The average score may be evaluated to see if it is significantly different from a score of 4 (No Change), using the Wilcoxon Signed Rank test.

11.2.3 FIQOL

The FIQOL is administered at Baseline and at 3, 6, 9, and 12 months. The following scoring algorithm is used to create subscale scores for Lifestyle (10 items), Coping/Behavior (9 items), Depression/Self Perception (7 items) and Embarrassment (3 items). Raw item scores are on a 5 point scale for Question 1 (1=Excellent to 5=Poor), 4 point scale for Questions 2a-2m (1=Most of the Time to 4=None of the Time), 4 point scale for Questions 3a-3n (1=Strongly Agree to 4=Strongly Disagree), and 6 point scale for Question 4 (1=Extremely So to 6=Not at All).

- Lifestyle is the average score for questions 2a, 2b, 2c, 2d, 2e, 2g, 2h, 3b, 3l, and 3m, where no more than 4 items are missing
- Coping/Behavior is the average score for questions 2f, 2i, 2j, 2k, 2m, 3c, 3h, 3j, and 3n, where no more than 4 items are missing
- Depression/Self Perception is the average score, where no more than 2 items are missing, of:
 - Question 1 (reverse coded to 5=Excellent to 1=Poor),

- Questions 3d, 3f, 3g, 3i, 3k
- Question 4, multiplied by 0.67 to rescale it to a 4-point range
- Embarrassment is the average score for questions 2l, 3a, and 3e, where no more than 1 item is missing

Subscale scores and their percent changes from baseline will be summarized by visit, based on the PP population.

Changes from baseline in subscale scores will be analyzed separately for each subscale score using a repeated measures model with baseline subscale score as a covariate. Least squares means and associated p-values may be presented for each timepoint during the Treatment Period.

All raw item scores may be listed by subject and visit. Subscale scores and their changes from baseline may be listed separately by subject and visit.

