3.3 Analysis Populations

The Safety Population will include all subjects exposed to any part of the Eclipse System during or after Visit 2 (Initial Fitting Visit). This will include all subjects who were unsuccessfully fitted, and screen failures. This will be the primary analysis population for all safety analyses.

The Intent-to-Treat (ITT) Population will include all subjects who are successfully fit with the Eclipse Insert, successfully complete Visit 4, and enter the Treatment Period.

The Per-Protocol (PP) Population will include all subjects in the ITT population who complete Visit 5 (Month 3 Visit), complete at least 10 out of 14 consecutive days of diary data at each time point in the study Treatment Period, and have no major protocol deviations.

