3.7 Secondary Effectiveness Analyses

The primary effectiveness analysis will be repeated for the 3, 6 month and 12 month time points on the PP population.

Changes from baseline will be evaluated at the 3, 6, 9 and 12 month time points, for the following effectiveness measures, also on the PP population:

- St. Mark's (Vaizey) Incontinence Severity Score
- FIQOL questionnaire subscales

PGI-I scores at 3, 6, 9 and 12 months (assessment not done at Baseline)

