11.2.4 St. Mark's (Vaizey) Incontinence Severity Score

The St. Mark's (Vaizey) Incontinence Severity questionnaire assesses seven aspects of incontinence severity (solid stool incontinence, liquid stool incontinence, gas incontinence, lifestyle alteration, the need to wear a pad or plug, taking constipating medicines, and lack of ability to defer defecation for 15 minutes).

An overall incontinence severity score, calculated and entered on the CRF, is derived as follows:

- The first 4 questions are scored on a 5-point scale, where 0=Never and 4=Daily
- The next 2 questions (wearing a pad or plug and taking constipating medicines) are scored where 0=No and 2=Yes
- The last question (deferring defecation) is scored where 0=No and 4=Yes
- The item scores are summed to create an overall score on a 24-point scale, where 0 is perfect continence and 24 is total incontinence.
- If any of the items used to create the overall score are missing, the score will be missing. (A missing FI bother item result will not affect the overall score).

An FI bother scale is also administered as part of this assessment. The amount that a subject's bowel control symptoms bothers her on the visit day is ranked on a 4-point scale, where 0=Not at all and 3=Greatly.

The severity score results, changes from baseline and/or percent changes from baseline may be summarized by visit. Changes from baseline in the severity score

will be analyzed using a repeated measures model with baseline severity score as a covariate. Least squares means and associated p-values may be presented for each timepoint during the Treatment Period.

The FI bother scale may be summarized by visit using the PP population. The change from baseline in the FI bother scale, which could take on values of -3 to 3 may also be summarized (continuously) and evaluated using the Wilcoxon Signed Rank test to determine if the average score is significantly different from zero (i.e., no change). The percent change from baseline in FI bother may be summarized as less bothersome (values <0), no change (0), or more bothersome (values >0) by visit.

The individual item scores, overall severity score, and FI bother scale may be listed by subject and visit.

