11.3 Additional Analyses of Diary Data

11.3.1 FI Episodes

The average number of FI episodes per week for each subject may be summarized by diary period (Baseline, Test, 3 month, 6 month, 12 month). The change from baseline and percent change from baseline may also be summarized for each Treatment Diary (3 month, 6 month, 12 month).

Percent changes from baseline will be analyzed using a repeated measures model with baseline average number of weekly episodes as a covariate. Least squares means and associated p-values will be presented for each timepoint during the Treatment Period.

The percent change from baseline in FI episodes will be further categorized by degree of improvement (<50% reduction, >= 50% reduction, >75% reduction, and 100% reduction) and the percent of subjects in each category summarized for each Treatment Diary. These analyses will be based on the PP population.

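### The PGI-I, FIQOL and FI-bother summaries and the stricter FI-episode categories have no ITT version, and the protocol and SAP define the per-protocol population differently

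*SAP*

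**What the plan says.** SAP 11 sets the rule: "The ITT population will be used as the primary analysis population for efficacy analyses", and "The PP population is used as a supportive analysis where specified".

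The individual sections then specify the following:

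- PGI-I (SAP 11.2.2): scores are summarised "both continuously and by number and percent of subjects selecting each response, using the PP population". The Wilcoxon test against a score of 4 names no population.
- FIQOL (SAP 11.2.3): "Subscale scores and their percent changes from baseline will be summarized by visit, based on the PP population". The repeated measures model names no population.
- St. Mark's (SAP 11.2.4): neither the severity summary nor the model names a population. For the bother item, "The FI bother scale may be summarized by visit using the PP population".
- FI episodes (SAP 11.3.1): after the improvement categories comes "These analyses will be based on the PP population". This covers at least the categories and perhaps the whole section.

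Protocol 3.7 places change from baseline in St. Mark's and FIQOL on PP: "for the following effectiveness measures, also on the PP population".

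The PP definitions differ. Protocol 3.3 requires that women "complete at least 10 out of 14 consecutive days of diary data at each time point in the study Treatment Period". SAP 7.2 asks for the same number of diary days at the 3-month visit only. SAP 8.2 and 11.2.1 exclude a woman with a missing response only at the time point she misses. SAP 10 names Protocol Revision D as its basis and declares no change in planned analysis.

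**The concern.** PGI-I, FIQOL and St. Mark's are named secondary endpoints (Protocol 3.5) in a study whose objective is durability. The SAP calls PP supportive, but for the summaries listed above there is no ITT analysis for it to support.

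The PP filter also fits questionnaires poorly. None of these instruments is scored from the diary, yet a woman who completed FIQOL and PGI-I at month 3 and kept only 9 diary days is removed. So is a woman whose deviation the sponsor classes as major before database lock (SAP 7.3), in an open-label single-arm trial. If such women did worse than average, the reported improvement is too favourable.

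Where no population is named, two programmers could produce different results. The SAP 11 default points to ITT, while Protocol 3.7 points to PP for FIQOL and St. Mark's change. On the ITT reading, the FIQOL table and the FIQOL least squares means for the same visit would describe different sets of women.

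Under the Protocol 3.3 definition, membership of the month-3 PP set would depend on diaries kept at 6 and 12 months, so an early result would be conditioned on later follow-up.

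**Working it through.** **1. Which analyses have an ITT version**

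| Analysis | Population in SAP | ITT version |
|---|---|---|
| PGI-I summary | PP | none |
| PGI-I Wilcoxon test | not named | by default only |
| FIQOL summary | PP | none |
| FIQOL model | not named | by default only |
| St. Mark's summary and model | not named | by default only |
| FI bother | PP | none |
| FI episodes, ≥50% reduction | PP | yes: this is the responder definition, analysed on ITT (SAP 8.2, 11.1, 11.2.1) |
| FI episodes, >75% and 100% | PP | none |

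**2. The plan's own figures** (Protocol 3.11, SAP 6.2)

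Inputs: 85.6% success among completers, 21.3% dropout by month 3, 33% dropout by month 12, ITT size 40 to 150.

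- ITT response: 0.856 × (1 − 0.213) = 0.674, stated as 67%.
- 12-month completers: 40 × 0.67 = 26.8 and 150 × 0.67 = 100.5, stated as about 25 to 100.

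Both reproduce.

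**3. Effect of the two PP definitions at month 3**, counting dropout only

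- SAP 7.2: at most 150 × 0.787 = 118.1, or 40 × 0.787 = 31.5.
- Protocol 3.3 read literally: at most 150 × 0.67 = 100.5, or 40 × 0.67 = 26.8.
- Difference: 150 × (0.787 − 0.67) = 17.6, about 18 women; 40 × 0.117 = 4.7, about 5 women.

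This treats everyone who reaches Visit 5 as otherwise eligible for PP. It is not an upper limit, because the literal definition also removes women who stay but record fewer than 10 diary days at month 6 or 12.

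For month-3 response among PP women, the SAP definition gives 85.6% on the plan's inputs. Under the literal protocol definition, the limits depend on who leaves between months 3 and 12. Responders at month 3 are 0.856 × 0.787 = 0.6737 of ITT, non-responders 0.1133, and later leavers 0.117.

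- All leavers were responders: (0.6737 − 0.117) / 0.67 = 83.1%.
- All non-responders leave: (0.6737 − (0.117 − 0.1133)) / 0.67 = 100%.

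These are extremes, not forecasts.

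**4. Effect of the PP filter on questionnaires**

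The documents give no count of women with a questionnaire whom PP would drop. As an illustration only, let r be that fraction of women with data, and k their mean change as a share of the retained women's mean change. Then

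PP mean ÷ available-data ITT mean = 1 / [(1 − r) + r × k].

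| r (assumed) | women of 118 | k = 0 | k = 0.5 | k = 1 |
|---|---|---|---|---|
| 0% | 0 | 1.000 | 1.000 | 1.000 |
| 2% | 2.4 | 1.020 | 1.010 | 1.000 |
| 5% | 5.9 | 1.053 | 1.026 | 1.000 |
| 8.2% | 9.7 | 1.089 | 1.043 | 1.000 |

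The last row borrows the whole ITT-to-PP loss in the LIFE study at 1 month, (61 − 56)/61 = 8.2% (Protocol 1.6.2). That loss includes non-completers, so it serves only as an assumed high end. Values of k below 0 or above 1 fall outside the table.

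**The case against.** Naming PP is not in itself a contradiction. SAP 11 permits PP where it is specified, and for the FIQOL summaries Protocol 3.7 says the same. This stands: the defect is the missing ITT version, not a breach of the rule.

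A reader might infer that the protocol and SAP openly disagree on the population for FIQOL and St. Mark's. The documents do not support that. The FIQOL summaries agree on PP, and the SAP never writes ITT for the models or for the St. Mark's summary. The FIQOL model and the PGI-I test come shortly after sentences naming PP, so PP is an equally possible reading. What can be said is that the population is not named and the two available pointers differ.

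It can also be argued that if silence means ITT, several of these analyses are already on ITT. That is true for the models, the St. Mark's summary and the PGI-I test. The PGI-I, FIQOL and FI-bother summaries would still be PP-only.

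FI bother is not a protocol endpoint and the FI-episode categories are additional analyses, so they weigh less. For diary measures the gain is small: SAP 8.2 already bars averages from diaries under 10 days, so at month 3 an observed-data ITT table adds essentially only women with major deviations.

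A reader might also take the 21.3% dropout as the share of women whom an ITT table would bring back. It is not. Women who left without completing a questionnaire stay missing under either population.

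**Conclusion.** The point holds in limited form. Three things are established from the text:

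- The PGI-I, FIQOL and FI-bother summaries and the >75% and 100% FI-episode rows have no ITT version.
- The two PP definitions conflict.
- The SAP 10 statement of no change is therefore incorrect.

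The definitional conflict is worth about 18 of 150 or 5 of 40 women at month 3, on the plan's own dropout rates and counting dropout alone. The size of the selection in the questionnaire results is unknown. The illustration gives a PP excess of 0% to 9%, but both of its inputs are assumed.

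The consequences are bounded. The primary test and the 6- and 12-month ITT responder analyses are unaffected, and all other p-values are descriptive (SAP 8.1). The change should be made, but the main conclusion of the trial does not depend on it.

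**What to change.** 1. In SAP 11.2.2 to 11.2.4, present PGI-I, FIQOL, St. Mark's and FI bother on ITT, using all available data by nominal visit (as in SAP 8.6), with PP as supportive. Report the number of ITT women with data at each visit.
2. In SAP 11.3.1, add an ITT version of the >75% and 100% rows, keep the 10-day diary rule of SAP 8.2, and state the denominator.
3. Name one population for each summary, model and test, and align Protocol 3.7.
4. Use the SAP 7.2 definition of PP in both documents, so that month-3 membership does not depend on later diaries.
5. Record these changes in SAP 10.

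The cost is wording in both documents and a second run of the same tables. No visits or data collection are added. Reported improvements may be slightly smaller. The change does not remove dropout bias.
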